3.1. Primary endpoints

The **primary objective** of the assessment study is to compare the acceptance and the performance of the AIDAVA prototype versus existing practice, and between the 2 versions of the prototype. To this end, we propose to measure the following endpoints that will be recorded across sites.

Objective	Primary Endpoints
Metric 1. Evaluate acceptance by end users	Metric definition: Structured questionnaire (adapted from a System Usability Scale with additional questions such as I would recommend AIDAVA to my friend, colleague, or family member I am interested / ready to work with AIDAVA when available on the market I understand the purpose of data curation I am ready to spend the needed time to ensure proper data curation The curation process was perfect/acceptable/too long for me Measurement score (M1) through structured questionnaire (System Usability Scale - form) provided in REDCap
Metric 2. Measure	Metric definition
impact on workload for quality enhancement of data (including quality of the different curation tools)	 Compare time spent in curating data in G0 (current situation) G1 (generation 1 of the prototype) G2 (generation 2 of the prototype). Check the amount of data curated in the average time: are there more data being curated together with the ones needed to support the use case
	 Measurement For estimated time spent in curating (M2.1) User entry in dedicated "Curator form" (RedCap) For curators, when requesting an estimate for G0, it is important to ensure that curated data set have the same level of complexity as for G1 and G2 complexity: Extract a sample (synthetic data ?) to be curated including several data sources; Request existing registry stewards to provide a time to curate data up to insertion into registry (M2.2) System check "active" time of user to answer a query Amount of additional data elements are curated automatically computed (M2.3) How many data elements have been curated automatically by the systems (M2.4) How many data elements have required human interventions and been successful answered by the patients (i.e. answer provided to the question)

Objective	Primary Endpoints
	 (M2.5) How many data elements have required human interventions can not be answered by the patients and are sent to the curators (M2.6) How many data elements send to the curators did not get appropriate answer to finish the curation process

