G1 and G2 VISIT 1 - on site W1 Day 1 (either elective outpatient clinic visit OR inpatient stay during index MI event),	 Approximately up to 50 inpatients screened, 15 inpatients enrolled (Note: Day1 and Day2 may seem busy for a patient recovering from MI; most patients are however recovering well and find difficult to remain in hospital during the monitoring period) 1. Checking I/E criteria (In REDcap) 2. Project introduction (10 min, doctor). Research associate complete REDCap Form (in REDCap, Patient Screening FORM) If the patient meets the criteria and is interested in participating in the project, he/she will move on to the research associate 3. Under supervision of Research Associate - 30-60 min per patient 	

	CVD patients	BC patients
	 a. Share details of the project with patients ; b. Provision of SIP and explanation - including use of EQ-5D QALY - quality of life questionnaire several time c. Introduction of HDI and questions regarding ownership and future use of the data through HDI d. Answer to questions e. Request to read and sign ICF and HDI agreement f. Provide medical device to patient 4. Research associate update REDCap Form (in REDCap, Patient Screening FORM) 5. Confirmation of patient enrollment; 	
	 Create HDI account (through AIDAVA) Questionnaire to specify user profile (In REDCap 3. Training session for the patient on the prototyp Patient fills EQ-5D form through HDI provided a Research associate complete REDCap Form (sources for enrolled patients Patient and expert curator curate medical data), User Profile FORM) e by the research associate pp in REDCap, Patient monitoring FORM) data extraction from different with AIDAVA
W1	CVD patient will use medical device	
Day 2 - 5	 Patient will use AIDAVA and test its functionalities, take notes and if necessary, will contact Helpdesk whenever needed Expert curator will curate the data in AIDAVA on demand. RA fill the patient monitoring form (in REDCap, Patient monitoring FORM) 	
W1 Day 5	 First calculation of SMART risk score by AIDAVA (automatically) and CVD expert (manually). Data collection and entry forms : Documentation of SMART risk score calculation result and time (in REDcap, Patient Monitoring FORM) by RA 	 System extracts the patient data for insertion into the local AIDAVA BC registry Queries identified as secondary end points will be fired automatically by the system and results available for display to the BC data users

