9.2 Analysis Sets

Primary endpoint components

The analysis set will include all expert curators and patient participants and will take into account the primary data points (PDP) identified in yellow in the figure below across the 3 arms.

Primary Data Point	Generation	Arm	Description of measures (through RedCap Form and computed)		
PDP1	G0		M2.1 : Estimated time spent in curation per patient record (min)		
PDP2	G1	Expert Curator	M1: System Usability Score M2.1: Estimated time spent in curation per patient record (min)		
PDP3	G2		Same than for G1 - measured for G2		
PDP4	G1	G1 AND G2 users	 M1: System Usability Score M2: Time spent in for curation in min Estimated time in RedCap form (M2.1) Computed "active" time to answer queries (M2.2) Computed amount of data elements curated automatically by system (M2.3) requiring human intervention with answer from the patient (M2.4) 		

Primary Data Point	Generation	Arm	Description of measures (through RedCap Form and computed)
			 without answer the patient and requiring curator input (M2.5) without answer requested from curator but not successful (M2.6)
			M3: Computed data quality scores of curated record in terms of completeness, correctness, consistency and trustworthiness (as detailed in Task 4.6).
			 M4: Computed quality of the NLP concept extraction against the manually annotated data ("gold standard") Precision (M4.1) which measures the fraction of gold standard instances among the retrieved instances Recall (M4.2) which measures the fraction of the gold standard concepts that could successfully be retrieved
PDP5	G2		Same than PDP4 - for G2
PDP6	G1	G1 OR G2	Same than PDP4 - for G1
PDP7	G2	users	Same than PDP5 - for G2

Secondary endpoints

The analysis set will include all data users (BC specialists and CVD experts) and will take into account the secondary data points (SDP) identified in orange in the figure below across the patient arms. As indeed this is about reuse of data, after the curation process; there is no effect expected from the fact that patients did use G1 before G2 or not.

Secondary Data Point	Generation	Arm	Description of measures (through RedCap Form and computed)		
			Breast Cancer		

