9.3 Statistical Analyses

Three tests have be retained

- **Paired t-test**: statistical test that compares the means of two related groups, where each subject is measured at two different time points or under two different conditions. It is used to determine if there is a significant difference between the two groups.
- Mann-Whitney U test (unpaired t-test): non-parametric statistical test used to compare the medians of two independent groups. It is often used when the data are not normally distributed or when the sample sizes are small.
- Wilcoxon signed-rank test: non-parametric statistical hypothesis test used to compare two populations with two matched samples.

Primary Endpoint(s) Analysis

The endpoints are defined in Section 9.2 will be used to support the analysis

Computed	Description of measures	Test & meaning (per H1)			
	Population: Expert Curators				
E1	Difference between data points 1 and 2: E1.M2.1△ = M2.1@PDP1 - M2.1@PDP2 E1.M2.2△ = M2.2@PDP1 - M2.2@PDP2	Paired t-test H1: less time spent in curation in G1 than in G0 for expert curators			
E2	Difference between data points 2 and 3: E2.M1-Δ = M1@PDP2 - M1@PDP3	Paired t-test H1: G2 is more usable than G1 for expert curators			
	E2.M2.1∆ = M2.1@PDP2 - M2.1@PDP3 E2.M2.2∆ = M2.2@PDP2 - M2.2@PDP3	H1: less time spent in curation in G2 than in G1 for expert curators			
	Population:	Patients			
P1	Difference in data points 4 and 5 (i.e. difference between G1 and G2 for arm where patients used G1 AND G2)	Paired t-test (effect of system + training/experience from G1)			
	P1.M1- = M1@PDP4 - M1@PDP5	H1: G2 more usable than G1			
	P1.M2.x∆ = M2.x@PDP4 - M2.x@PDP5	H1: G2 requires less time for curation than G1 H1: G2 enables curation with less human intervention than G1			
	P1.M3-∆ = M3@PDP4 - M3@PDP5	H1: G2 provide same or higher quality than G1			
P2	Difference in data points 6 and 7 (i.e. difference between G1 and G2 for arm where patients used G1 OR G2)	Unpaired t-test (effect of system only)			
	P2.M1- = M1@PDP6 - M1@PDP7	H1: G2 more usable than G1			
	P2.M2.x∆ = M2.x@PDP6 - M2.x@PDP7	H1: G2 requires less time for curation than G1 H1: G2 enable curation with less human intervention than G1			
	Ρ2.Μ3-Δ = M3@PDP6 - M3@PDP7	H1: G2 provide same or higher quality than G1			

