9.4 Sample Size Determination

We expect a minimum of 15 patients per site and per use case, for a total of 90 patients and 12 data curators across the 2 use cases.

The main objective of the study is to assess performance and acceptance of the AIDAVA prototype and provide evidence that the overarching approach - and underlying tools - can open to new possibilities in data quality enhancement and FAIRification of the data. For this proof of concept study, it is assumed that between 50 to 80 subjects will be sufficient. As we expect some drop out between the 2 epochs of the study, for G1 and for G2 of the prototype, we targeted a higher number than needed.

	Use case 1 Health record of cardiac patients	Use case 2 Breast Cancer Patient registry		
NEMC -	15 patients	15 patients		
MIDATA	+3 expert data curators			
MedUniGraz -	15 patients	15 patients		
MIDATA	+3 expert data curators			
MUMC+/Maastro -	15 patients (MUMC)	15 patients (Maastro)		
DIGI.me	+3 expert data curators			
TOTAL	45 patients	45 patients		
	+ 9 expert data curators			

10. Supporting Documentation and Operational Considerations

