2. For me it is important to know, who has curated my health data and which tools have been used during the curation	Э	Strongly disagree	Strongly agree	
process.	>	Change the slider	above to set a response	
				reset
In my opinion, information regarding this aspect is sufficient in	θ	Strongly disagree	Strongly agree	
* must provide value	$\overline{\varphi}$	Change the slider	above to set a response	
				reset
3. For me it is important to know, whether a health data	Э	Strongly disagree	Strongly agree	
* must provide value	>	Change the slider	above to set a response	
				reset
In my opinion, information regarding this aspect is sufficient in	θ	Strongly disagree	Strongly agree	
In my opinion, information regarding this aspect is sufficient in AIDAVA. * must provide value	H	Strongly disagree	Strongly agree above to set a response	

AIDAVA specific questions				
1 I would recommend AIDAVA to my friend colleague or family	e P	Strongly disagree	Strongly agree	
member.		Change the slider abo	ove to set a response	reset
2. Lam ready to work with AIDAVA when available on the) P	Strongly disagree	Strongly agree	
market.		Change the slider above to set a response		reset
	Ē	Strongly disagree	Strongly agree	
3. I understand the purpose of data curation.		Change the slider above to set a response		reset
4. I am ready to spend the needed time to ensure proper data curation of my data.		Strongly disagree	Strongly agree	
		Change the slider abo	ove to set a response	reset
5. This system is unique and different from anything else	Ð (þ	Strongly disagree	Strongly agree	
available.		Change the slider abo	ove to set a response	reset
6. This system will allow me to manage my health records	E (Strongly disagree	Strongly agree	
better.		Change the slider abo	ove to set a response	reset
Please write down any suggestions you might have on how we could improve/ make AIDAVA easier to use.	θ			
	\bigcirc			
				Expand

Expert Data curators Form

Form to be used by the expert curator to enter performance metrics needed to assess the AIDAVA prototype in G1 and G2.

Expert Data Curator Form - G1 & G2					
Generation of the prototype		8 Q	O Generation 1 O Generation 2		reset
Site name:) (O NEMC - Sihtasu O UM - Maastrich O MUG - Medizini	tus Põhja-Eesti Regionaalhai t University sche Universität Graz	igla reset
Expert Curator ID / pseudonym:		~			
Number of patients supported:		(example:	0 or 12)		
Period of time during which patient rec	ords were supported				
Start:			Today Y-M	-D	

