Week 13 Week 14 G2 - Total Time (ingestion and M2 Estimated time spent working Week: Week 1 Week 2 Week 3 Week 3 Week 4 Week 5 Week 5 Week 6 Week 7 Week 8 Week 8 Week 9 Week 10 Week 11 Week 12 Week 13	2026-05-03 - 2026-05-09 curation): Date: 2026-02-01 - 2026-02-07 2026-02-08 - 2026-02-07 2026-02-15 - 2026-02-14 2026-02-15 - 2026-02-21 2026-02-15 - 2026-02-21 2026-03-01 - 2026-03-07 2026-03-01 - 2026-03-07 2026-03-08 - 2026-03-14 2026-03-15 - 2026-03-14 2026-03-15 - 2026-03-21 2026-03-29 - 2026-03-28 2026-03-29 - 2026-04-04 2026-04-05 - 2026-04-11 2026-04-12 - 2026-04-18 2026-04-19 - 2026-04-18 2026-04-26 - 2026-05-02	View equation Ing, visit, visualization): Hours:

For Generation 2

This form is linked with a table that contains all the metrics manually entered in REDCap (as .csv-export) that are needed to evaluate the system from an expert curator perspective.

Record ID record_id	Generation of the prototype generation_edcf_2	Site name: site_name_edcf_2	Expert pseudor pseudor	curator ID / nym: nym_edcf_2		
MUG BC Test	IG BC Test Generation 1 (1) MUG - Medizinische Universität Graz (3)		MUGBCC4 (2)			
MUG CVD Test	Generation 2 (2)	MUG - Medizinische Universität Graz (3)	MUGC	VC3 (1)		
G1 - Total Time (in in minutes: edcf_2_g1_total_min	gestion and curation) 🔶	G1 - Total Time (training, visit, visualiza in minutes: edcf_2_g1_total_min_2	tion) 🍦	G2 - Total Time (ingestion in minutes: edcf_2_g2_total_min	n and curation) 🛛 🍦	G2 - Total Time (training, visit, visualization) in minutes: edcf_2_g2_total_min_2
2160		4200				
				2580		3780

Patient Data curators Forms

Form to be used by the patient - as a curator - to enter performance metrics needed to assess the AIDAVA prototype in G1 and G2.

Patient Data Curator Form - G1 & G2	
Generation of the prototype	B ○ Generation 1 ○ ○ Generation 2 reset
Site name:	 NEMC - Sihtasutus Põhja-Eesti Regionaalhaigla UM - Maastricht University MUG - Medizinische Universität Graz
Therapeutic Area:	 Breast Cancer ○ Cardiovascular
Patient ID / pseudonym:	MUGCVP1
Period of curation:	
Start:	2023-09-01 Today Y-M-D
End:	2023-09-14 31 Today Y-M-D

ay:	Date:	Hours	:	Minutes
ay 1	2023-09-01 View equation	2	:	15
ay 2	2023-09-02 View equation	3	:	00
ay 3	2023-09-03 View equation	5	:	45
y 4	2023-09-04 View equation	5	:	30
y 5	2023-09-05 View equation	1	:	10
y 6	2023-09-06 View equation	2	:	05
7	2023-09-07 View equation	1	:	00
8	2023-09-08 View equation	3	:	30
9	2023-09-09 View equation	4	:	00
10	2023-09-10 View equation	1	:	00

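### E1, the only primary comparison with current practice, omits patient time, so work moved from curators to patients counts as time saved

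*Protocol*

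**What the plan says.** The primary alternative hypothesis in section 9.1 is that G1 makes curation and publishing more efficient than the current situation, and that the gain comes mainly from the tool. Time (M2) is named there as one of two critical metrics.

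The G0 contrast is E1 in section 9.3: M2.1 at PDP1 minus M2.1 at PDP2, expert curators only, paired t-test, with "H1: less time spent in curation in G1 than in G0 for expert curators". E1 also lists M2.2, but section 9.2 defines only M2.1 as a time measure for curators at these two data points, so E1 rests on M2.1.

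- **G0 time.** Section 9.2 defines M2.1 as "Estimated time spent in curation per patient record (min". Section 3.1 describes how it is obtained: "Request existing registry stewards to provide a time to curate data up to insertion into registry". Section 9 limits the G0 analysis to the curator arm.
- **G1 time.** M2.1 is again per record and for the curator. Section 4.4.2 says of the days between visits: "Expert curator will curate the data in AIDAVA on demand". The curator form in 10.3.3 collects weekly hours and "Number of patients supported".
- **Patient time at G1 and G2.** It has its own form in 10.3.3: "Form to be used by the patient - as a curator - to enter performance metrics needed".
- **Number of curators.** The text of 9.4 says "for a total of 90 patients and 12 data curators across the 2 use cases"; the table below it totals "9 expert data curators".

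**The concern.** The two terms of E1 do not cover the same share of the work. At G0 one person, the steward, does the job through to the registry. At G1 the patient ingests and curates (section 2.2, Steps 1 and 2), the system directs questions to patient or curator (section 2), and items that patients cannot answer go on to the curator (M2.5, section 3.1). The G0 instruction in 3.1 asks for data of matching complexity; it does not match who does the work.

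A drop in curator minutes can therefore come from automation, from patients doing the work, or from both, and E1 cannot tell these apart. Section 9.1 attributes the gain mainly to the tool. A significant E1 could be reported as support for that claim when human time per record has not fallen.

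**Working it through.** **1. Which primary analyses use G0?** E2, P1, P2, A3 and A4 compare G1 with G2 or the patient arms with each other; A1 and A2 are descriptive for G1 and G2. M3 is computed only at G1 and G2 (section 3.1). Section 3.1 foresees a G0 count for M4, but no analysis in 9.3 uses it. Only E1 remains.

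**2. What E1 measures.** The protocol gives no effect size, SD, alpha or power for E1, so there is no planned figure to reproduce. Let

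- T = curator minutes per record at G0,
- a = share of T that the tool removes,
- p = share of the remaining work done by patients,
- k = patient minutes needed per curator minute.

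At G1 the curator spends T(1−a)(1−p) and the patient T(1−a)pk. So

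- E1 = T − T(1−a)(1−p),
- saving in total human time = E1 − T(1−a)pk.

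E1 exceeds the human-time saving by exactly the patient minutes, and the two agree only when p = 0. With T = 100 (illustrative):

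| a | p | k | E1 | Total human time saved |
|---|---|---|---|---|
| 0 | 0.25 | 1 | 25 | 0 |
| 0 | 0.50 | 1 | 50 | 0 |
| 0 | 0.75 | 1 | 75 | 0 |
| 0.2 | 0 | any | 20 | 20 |
| 0.2 | 0.50 | 1 | 60 | 20 |
| 0.2 | 0.50 | 2 | 60 | −20 |

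**3. How often E1 would favour G1 when the tool saves nothing.** Assume a = 0, k = 1, a two-sided 5% paired t-test, and an SD of the paired difference equal to a fraction c of T. The noncentrality parameter is (p/c)√n. For n = 9 and p = 0.50 it is (0.50/0.30)×3 = 5.0, (0.50/0.50)×3 = 3.0 and (0.50/1.00)×3 = 1.5. The probability of a significant result in favour of G1 is:

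| n | p | c = 0.30 | c = 0.50 | c = 1.00 |
|---|---|---|---|---|
| 9 | 0.10 | 0.14 | 0.08 | 0.05 |
| 9 | 0.25 | 0.59 | 0.26 | 0.10 |
| 9 | 0.50 | 0.99 | 0.75 | 0.26 |
| 12 | 0.25 | 0.75 | 0.35 | 0.12 |
| 12 | 0.50 | 1.00 | 0.88 | 0.35 |

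The nominal rate in that direction is 0.025. More curators make the problem worse, because it is a bias and not a lack of precision.

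**4. Curator count.** Three sites × 3 curators = 9, as in sections 1.1 and 4.1 and the 9.4 table. Twelve would need four groups of three; the table has three, with MUMC+/Maastro sharing one.

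**The case against.** The best defence is that E1 is honest about its scope. Its hypothesis is worded for expert curators, Metric 2 is about workload, and lower curator workload is a stated benefit in section 2.3. Patient time is described in A1 and A2 and compared between generations. This stands: E1 is a valid measure of curator burden. It does not rescue E1 as the sole support for the broader claim in 9.1.

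A second objection also stands in part. G0 time stops at registry entry, while patient time at G1 may cover GP, app and device data that the registry record does not need. Adding patient minutes could then overstate human time at G1.

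Four stronger readings are tempting and not supported:

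- **That E1 is the only test of any kind against current practice.** U0 in 9.3 is a secondary G0–G1 test, but of breast cancer query time, effort and accuracy, not of curation.
- **That curator time at G1 is purely residual.** Patient and curator both curate at visits (4.4.2), and the curator may act as the patient's deputy (2.2).
- **That total human time rises many-fold.** The minutes shown in the 10.3.3 form examples are test entries, so no ratio can be drawn from them.
- **That a curator total left undivided by patients would add to the bias in favour of G1.** It would raise the G1 term and so lower E1. In any case M2.1 is already defined per record and its denominator is collected.

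**Conclusion.** The point holds for the primary analyses. E1 is the only one that uses G0, and it counts curator time alone while part of the work moves to patients. Any such transfer raises E1 by the curator minutes moved, whether or not human time is saved. The size depends on the share moved and on the spread of the paired differences, neither of which the protocol gives. Under the assumptions above, the chance of a spurious result favouring G1 with nine curators runs from 0.05 (10% moved, SD 100% of G0 time) to 0.99 (50% moved, SD 30%), against 0.025. The direction of the bias needs no assumption beyond some transfer taking place. E1 can support a statement about curator workload; it cannot by itself support the efficiency claim in 9.1 or the attribution of the gain to the tool. Separately, the 12 curators in the text of 9.4 contradict its table and the design, which give 9.

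**What to change.** 1. In 9.3, keep E1 and label it a curator-workload measure. State that it is not used alone to support the efficiency hypothesis in 9.1.
2. Add a G0–G1 and a G0–G2 comparison of total human minutes per record, defined as patient ingestion and curation minutes (Form 11) plus curator ingestion and curation minutes (Form 10 total ÷ patients supported). Average the patient minutes within the curator named for each patient on the Visit 1 form, so that each curator's value pairs with that curator's G0 minutes per record.
3. Report this beside the curator-only result, with the caveat that patient time may cover more data than the registry record.
4. In the text of 9.4, change 12 curators to 9.

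The cost is analysis wording. The G1 and G2 patient and curator minutes, the number of patients supported and the patient–curator link are already on the forms, and G0 minutes per record are already specified in 9.2. The price for the sponsor is that the efficiency result may look less favourable.

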1.1. Synopsis

Study Title	Assessment study of the AIDAVA prototype which aims to improve the quality of clinical data, for their reuse in clinical care in patients with established cardiovascular diseases, and in clinical research for breast cancer research.											
Rationale	 to curate and publish their personal data in a secure environment, generating an interoperable and reusable personal medical record that can be used in clinical care to improve patient outcomes and to support data driven clinical research. The assessment study will help to determine whether the AIDAVA intelligent virtual assistant is 1. effective in improving data curation and publishing process against existing practices, 2. usable and acceptable by patients - with different levels of health, digital and data literacy - and expert data curators, whenever their input is required, 3. valuable for "data users" such as cardiovascular treating physicians and breast cancer clinical researchers. The efficacy of AIDAVA virtual assistant will be influenced by the quality of the different data curation tools (supporting automation) and by the explainability module (managing the human computer interaction). The study will help identify how these components impact the effectiveness of the device. 											
	The results of the study will be used to inform the exploitation plan of the prototype, and the needed improvement to bring a final device to the market.											
Overall Design	 Three arms, prospective cohort-study involving 30 patients per site, 15 Breast Cancer (BC) and 15 cardiovascular (CVD) + 3 experienced data curator per site based on already collected health data, available across different data sources with 3 arms: one for patients assessing the prototype across the 2 generations⁶, one for the patients assessing the prototype only for a single generation, and one for the expert curators (assessing the prototype across the 2 generations) across 4 epochs (see Figure 1) Epoch 1: 1 week duration, takes place just before deployment and evaluation of Generation 1 (G1) of the prototype; it will allow to gather information from the curator on the current situation. 											
	 Epoch 2: 2 weeks duration per patient during period of July - September 2024: assessment of G1, by ingesting personal health data into the prototype and curating them 											

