4.1 Overall Design

The assessment study will be a cohort, 3 arms, prospective¹³ study involving 30 patients (15 breast cancer and 15 CVD) + 3 expert curators in each site. It will be based essentially on available data, collected during clinical care (see Section 10.1 for detailed description of data sources), but will also include some prospective data from medical devices and Quality of Life questionnaire

There will be 3 arms that will allow comparison across these different populations of users.

- "G1 and G2" patients who contributed to evaluation of G1 and G2.
- "Single Generation" patients who contribute to the evaluation of only one generation of the prototype (G1 or G2)
- Expert data curators

There will be 4 epochs

- Epoch 1 will last 1 week and take place just before deployment and evaluation of G1; it will allow to gather information from the expert curator on the current situation/curation process and to provide a dedicated training to the curators.
- Epoch 2 will last for 2 weeks, and is expected to take place in the period of July September 2024. Patients will be requested to ingest their data with the support of the prototype, and to curate them. Whenever needed, the data expert curator will be able to support them.
- Epoch 3 will last for 16 to 18 months: "wash out" period during which G2 of the prototype will be developed;
- Epoch 4 will last for 2 weeks and is expected to take place in the period February/March 26. Patients and curators will be requested to assess Generation 2 (G2) of the prototype, by performing the same task as in Epoch 2 to enable comparison of the performance of the 2 generations of the prototype.

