4.4.4. Returning patients (for G2 only)

This is applicable only for patients who have participated to the assessment of G1 and are also assessing G2

	CVD patients	BC patients
2 weeks for start G2: Jan 2026	Refresh training of Expert curators and Research associates	
G2 VISIT 1 - on site W1 Day 1	 Upload of all data (starting from scratch) Patient will be called in for outpatient visit by the res Questionnaire to specify user profile (In Redcap, Use Training session for the patient on the prototype - G Patient fills EQ-5D QALY - quality of life questionnaire Research associate complete REDCap Form (in REDC Patient and expert curator curate medical data with 	search associate er Profile FORM) 2 version - by the research associate (2,5h) e through HDI provided app ap, Patient monitoring FORM) for enrolled patients AIDAVA
W1 Day 2-5	 CVD patient use the medical device Patient will use AIDAVA and test its functionalities, ta Expert Curator will curate the data in AIDAVA, on der RA fill the patient monitoring form (in REDCap, Patient) 	ake notes and if necessary, will contact helpdesk mand ent monitoring FORM)

	CVD patients	BC patients
W1 Day 5	 First calculation of SMART risk score by AIDAVA (automatically) and CVD expert (manually). Data collection and entry forms documentation of SMART risk score calculation result and time (in REDCap, Patient monitoring FORM) 	 System extracts the patient data for insertion into the local AIDAVA BC registry Queries identified as secondary end points will be fired automatically by the system and results available for display to the BC data users
	 AIDAVA extract IPS and forward it automatically to th Data curators spreadsheet (Patient as curator and E Form) Data user/consumers spreadsheet (In REDCap, Data 	ne HDI (+ enter flag in REDCap, Patient monitoring Form) Expert Curator). (in REDCap, Patient Curator FORM; Expert Data Curator user/consumer Form)
VISIT 2 - online W2 Day 1	CVD patients use medical device Check if there is any issue with the medical device (CVD patient only)	
	 Second training session on the prototype - online (open questions) Patient and expert curator curate medical data using AIDAVA RA fill the patient monitoring form (in REDCap, Patient monitoring Form) 	
W2	CVD patient use the medical device	

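### Curator experience is mixed into E2, and into P2 for M2.6 and probably M3, but the labels in 9.3 do not say so

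*Protocol*

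**What the plan says.** The synopsis (1.1) defines three arms, among them "one for the expert curators (assessing the prototype across the 2 generations"). There is no group of curators who meet G2 for the first time. Section 4.1 has patients and curators assess G2 "by performing the same task as in Epoch 2 to enable comparison of the performance of the 2 generations of the prototype", and section 4.4.4 schedules "Refresh training of Expert curators and Research associates" shortly before G2.

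Section 9.3 sets out the contrasts that matter here:

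- **E2** (curators, G1 versus G2) is a paired t-test on usability and time. For time it is read as "H1: less time spent in curation in G2 than in G1 for expert curators". No experience term or caveat is attached.
- **P1** (patients who used both generations) is also paired and is labelled "effect of system + training/experience from G1".
- **P2** (patients who used one generation only) is unpaired and is labelled "effect of system only". It covers M1, all of M2.x and M3.
- **A4** is P1 minus P2 and is described as the effect of the patients' own experience.

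M2.6 is defined in 3.1 as "How many data elements send to the curators did not get appropriate answer to finish the curation process" and repeated in 9.2 as "without answer requested from curator but not successful (M2.6"). M3 scores the curated record, on which curators work on demand (4.4.2). Its formula is left to another deliverable (3.1, Metric 3). Section 9.1 names M2 and M3 as the two critical metrics. H1 there attributes the gain chiefly to the tool and a lesser part to training.

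**The concern.** For patients, the protocol recognises that a repeated-use comparison mixes the new release with what users learned on the old one, and it adds a single-generation arm to separate the two. Curators face the same problem, but they have neither the caveat nor a comparison group.

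This matters because H1 divides the improvement between tool and training. If curators are faster or leave fewer elements unresolved at G2 because they have used AIDAVA before, E2 and the curator-dependent part of P2 will show it as a G2 improvement. For P2 the printed label would assign it to the system. The error leans towards confirming H1, on the two metrics that the protocol calls critical.

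**Working it through.** **No planned figure to reproduce.** The protocol states no significance level, power, effect size, standard deviation or size of learning effect. The main check is therefore algebraic; the sizes below are illustrations.

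**1. What each contrast contains.** Let S be the system effect, Lp patient learning and Lc curator learning, each counted as an improvement from G1 to G2. For a patient-record measure that depends on curator action:

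- P1 = S + Lp + Lc
- P2 = S + Lc
- A4 = P1 − P2 = Lp

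For the curators' own measures, E2 = S + Lc.

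Example with S = 0, Lp = 10, Lc = 5 on an arbitrary scale: E2 = 5, P1 = 15, P2 = 5, A4 = 15 − 5 = 10. P2 shows a system-only effect of 5 when the true one is 0. A4 returns patient learning correctly. Lc is not estimated anywhere.

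**2. Which P2 measures depend on curators.**

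| Measure | Depends on curator action? |
|---|---|
| M1, M2.1, M2.2, M2.4 | Not directly: patient usability, patient time, elements answered by the patient |
| M2.3 | No: elements curated automatically |
| M2.5 | No: counted when the element passes to the curator, before the curator acts |
| M2.6 | Yes: elements the curator could not resolve |
| M3 | To the extent that the score reflects curator work; the formula is not in this document |

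**3. How large E2 could be with an unchanged tool.** Inputs: 90 patients and 9 curators (table in 9.4), so 90 / 9 = 10 records per curator per generation. The text of 9.4 says 12 curators, which would give 90 / 12 = 7.5; the table below uses 10. Assumed learning curve: time for record n is t(n) = n^(log2 r), so each doubling of records multiplies time by r. The values r = 0.95, 0.90 and 0.80 are assumptions.

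The reduction is 1 − (mean time over G2 records) / (mean time over G1 records). For r = 0.80 with no prior practice and full retention, the mean over records 1–10 is 0.632 and over records 11–20 is 0.417, so the reduction is 1 − 0.417/0.632 = 34%.

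| Starting point and retention | G1 records | G2 records | r = 0.95 | r = 0.90 | r = 0.80 |
|---|---|---|---|---|---|
| Any start, no retention | same position on the curve | same position on the curve | 0% | 0% | 0% |
| No prior practice, half retention | 1–10 | 6–15 | 6% | 12% | 24% |
| No prior practice, full retention | 1–10 | 11–20 | 9% | 17% | 34% |
| Practice worth 10 records, half retention | 11–20 | 16–25 | 2% | 4% | 9% |
| Practice worth 10 records, full retention | 11–20 | 21–30 | 4% | 7% | 15% |

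**4. How often E2 would be significant with no tool effect.** Paired t-test, assumed two-sided 0.05, noncentral t with noncentrality d√n, where d is the learning effect in standard deviations of the paired difference (assumed):

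| d | n = 9 | n = 12 |
|---|---|---|
| 0.25 | 10% | 12% |
| 0.5 | 26% | 35% |
| 0.8 | 56% | 71% |
| 1.0 | 75% | 88% |

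Nothing comparable can be computed for M2.6 or M3.

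**The case against.** The strongest reply is that the protocol claims less than a hurried reader might take from it. Four stronger readings are tempting, and the documents do not support them.

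- **That the protocol calls E2 a pure system effect.** It does not. The label "effect of system only" belongs to P2 alone. E2's hypothesis states a direction, not a cause; P1 uses similar hypothesis wording; and the general H1 concedes some effect of training without limiting it to patients. E2's fault is a missing caveat.
- **That A4 is biased.** It is not. A4 is described as patient experience, and the algebra shows that this is what it gives. It simply has no curator counterpart.
- **That P2 as a whole is contaminated.** Only M2.6 is directly affected among the six M2 measures, and M3 only so far as its unstated formula responds to curator work.
- **That the bias is known to be large.** The interval is 16 to 18 months, and retention could be nil. Curators are existing staff who curate regularly (4.3), and they are trained, with practice exercises, before using the prototype (4.4.1 and Annex 3), so much of the steep part of the curve may precede G1.

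These points narrow the finding and lower the likely size. They do not remove it. The protocol nowhere says that curator learning is lost over the interval, and its P1 and A4 allow for patient experience carrying across the same interval. The labels and contrasts are fixed in 9.3 itself, so this is not a detail left to a later analysis plan.

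**Conclusion.** The point stands in a limited form. E2 estimates system plus curator experience and should say so. P2's system-only label is wrong for M2.6, and for M3 to the extent that curators shape the score. No listed analysis separates curator learning from the tool. This follows from the design and the definitions and needs no outside figure.

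The size is not derivable from the documents. Under the assumed learning rates it runs from 0% to about 34% of curator time, and to about 15% at most if curators begin with practice worth 10 records. These figures concern curator time in E2 and rest on 10 records per curator per generation. They do not show that any observed G2 gain would be spurious, only that E2 could not tell the two sources apart.

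**What to change.** In section 9.3:

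1. Label E2 as *system + curator experience*, in line with P1, and do not use E2 alone to support H1's claim that the gain comes mainly from the tool.
2. Within P2, keep "effect of system only" for measures that do not depend on curator action (M1 and M2.1 to M2.5), and label M2.6 and M3 *system + curator experience*.
3. Leave A4 as it is, and state that it concerns patients only.

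It would be tempting to add a comparison of each curator's last G1 records with the first G2 records. That should not be added. Per-record curator times are not shown to be captured: the curator form in 10.3.3 asks for weekly hours, and 9.2 lists only M1 and M2.1 for curators although the E2 formula also uses M2.2. The comparison would also bring in forgetting over 16 to 18 months, a bias against G2.

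The cost is wording only, with no new participants, visits or data. The downside is that E2, and P2 for M2.6 and M3, support a weaker statement.
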